7.1.1 Screening Period

The subject's eligibility will be assessed at a Screening Visit that will occur within 42 days prior to Day 1. After providing written informed consent, the assessments described in [Table 1](#) will be performed.

If at screening, the subject meets all of the protocol inclusion and none of the exclusion criteria (including complete history of immunosuppressive, immunomodulating, and potential scleroderma disease-modifying medications as well as history of other medications in the previous year), the subject will be considered as eligible and will be enrolled in the trial and randomized. Subjects who fail to meet the protocol-specified criteria for randomization or dosing, or withdraw their consent before randomization, are considered screening failures. If the Investigator feels a particular screening assessment is aberrant and retesting could confirm eligibility, these may be repeated under the same subject number, provided the retest is performed within the same screening period. A subject who was considered a screen failure may be re-screened (only once per subject). Re-screening is not encouraged. However, on a case-by-case basis with permission of the Medical Monitor and the Sponsor's Medical Director, a subject who has not met all of the eligibility criteria within the original screening period may be permitted to be re-screened one time. An HRCT would not need to be repeated if completed within 2 months of the re-screening visit. Any TB test, including negative TB skin test with purified protein derivative, QuantiFERON-TB, or T-SPOT, would not need to be repeated if completed within 3 months of the re-screening visit. Each subject must be re-consented before re-screening occurs. A new subject number will be assigned and all screening assessments have to be repeated.

The following information, as a minimum should be collected for screen failure subjects: informed consent, demographics, reason for screen failure, AEs from the date of informed consent until subject is considered screen failure by the Investigator, and the Investigator's signature.

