7.4.1 Adverse Events

7.4.1.1 Adverse Event Definitions

Adverse Event

An AE is any untoward medical occurrence in a subject or clinical investigation subject administered a pharmaceutical product, regardless of causal relationship with this treatment. An

AE can therefore be any unfavorable and unintended sign (including an abnormal laboratory finding), symptom, or disease temporally associated with the use of a medicinal product, whether or not considered related to the IMP.

A TEAE is defined as any event not present prior to the initiation of the IMP or any event already present that worsens in either severity or frequency following exposure to the IMP.

For surgical or diagnostic procedures, the condition/illness leading to such a procedure is considered as the AE rather than the procedure itself.

The Investigator is required to grade the severity or toxicity of each AE.

Investigators will reference the National Cancer Institute (NCI) - CTCAE, Version 4.03 (publication date: 14 June 2010), a descriptive terminology that can be used for AE reporting.

A general grading (severity/intensity; hereafter referred to as severity) scale is provided at the beginning of the above referenced document, and specific event grades are also provided.

If a particular AE's severity is not specifically graded by the guidance document, the Investigator is to use the general NCI-CTCAE definitions of Grade 1 through Grade 5 following his or her best medical judgment.

The 5 general grades are:

- Grade 1 or Mild
- Grade 2 or Moderate
- Grade 3 or Severe
- Grade 4 or Life-threatening
- Grade 5 or Death.

According to Sponsor convention, any clinical AE with severity of Grade 4 or 5 must also be reported as an SAE. However, a laboratory abnormality of Grade 4, such as anemia or neutropenia, is considered serious only if the condition meets one of the serious criteria described below.

If death occurs, the primary cause of death or event leading to death should be recorded and reported as an SAE. "Fatal" will be recorded as the outcome of this specific event and death will not be recorded as separate event. Only, if no cause of death can be reported (for example, sudden death or unexplained death), the death per se might then be reported as an SAE.

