- Is otherwise considered to be medically important. (Note: Important medical events that may not result in death, be life-threatening, or require hospitalization may be considered as SAEs when, based upon appropriate medical judgment, they may jeopardize the subject or may require medical or surgical intervention to prevent one of the outcomes listed above. Examples of such events include allergic bronchospasm requiring intensive treatment in an emergency room or at home, blood dyscrasias, or convulsions that do not result in inpatient hospitalization, or the development of drug dependency or drug abuse.)

For the purposes of reporting, any suspected transmission of an infectious agent via an IMP is also considered an SAE, as described in Section 7.4.1.4.

Events that Do Not Meet the Definition of an SAE

Elective hospitalizations to administer, or to simplify trial treatment or trial procedures (for example, an overnight stay to facilitate chemotherapy and related hydration therapy application) are not considered SAEs. However, all events leading to unplanned hospitalizations or unplanned

prolongation of an elective hospitalization (for example, undesirable effects of any administered treatment) must be documented and reported as SAEs.

Events Not to Be Considered as AEs/SAEs

Medical conditions present at the initial trial visit that do not worsen in severity or frequency during the trial are defined as Baseline Medical Conditions, and are not to be considered AEs.

However, if adverse signs or symptoms occur in association with disease progression then these should be recorded as AEs.

Adverse Events of Special Interest

All blistering or Grade ≥ 3 AEs in the skin and subcutaneous tissue disorders SOC will be designated as AESI. Any cutaneous reaction of Grade 1 or 2 that is not responding to specific treatment or is worsening will also be designated as an AESI. The occurrence of cutaneous AESI or SAEs will be reviewed by an independent panel of dermatologists to provide guidance for further investigation and interpretation of these events, and advise the IDMC whether any actions to modify clinical trial conduct should be considered.

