7.4.1.3 Definition of the Adverse Event Reporting Period

The AE reporting period for safety surveillance begins when the subject is initially included in the trial (date of first signature of first informed consent) and continues through the post-treatment Safety Follow-up Period.

Any SAE assessed as related to IMP must be reported whenever it occurs, irrespective of the time elapsed since the last administration of IMP.

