Any trial treatment related grade >=3 treatment emergent AESI	xxx (xx.x)	xxx (xx.x)	xxx (xx.x)
Any trial treatment related grade >=4 treatment emergent AESI	xxx (xx.x)	xxx (xx.x)	xxx (xx.x)
Any treatment emergent AESI leading to death	xxx (xx.x)	xxx (xx.x)	xxx (xx.x)
Any trial treatment related treatment emergent AESI leading to death	xxx (xx.x)	xxx (xx.x)	xxx (xx.x)

NCI-CTCAE version 4.03.

Note: TEAEs are defined as events that start within the day of first dose of trial treatment until 28 days after last dose of treatment.

Related TEAEs are events with relationship missing, unknown or related.

AESI = Adverse Event of Special Interest.

15.3: Safety Data

15.3.1: Display of Adverse Events

Table 15.3.1.2: Overview of TEAEs Leading to Discontinuation / Dose Reduction of Treatment - SAF Analysis Set

Number of Subjects with:	Treatment A N=xxx (100%) n (%)	Treatment B N=xxx (100%) n (%)	Treatment C N=xxx (100%) n (%)
Any TEAE leading to temporary discontinuation of trial treatment	xxx (xx.x)	xxx (xx.x)	xxx (xx.x)
Any trial treatment related TEAE leading to temporary discontinuation of trial treatment	xxx (xx.x)	xxx (xx.x)	xxx (xx.x)
Any TEAE leading to permanent discontinuation of trial treatment	xxx (xx.x)	xxx (xx.x)	xxx (xx.x)
Any trial treatment related TEAE leading to permanent discontinuation of trial treatment	xxx (xx.x)	xxx (xx.x)	xxx (xx.x)
Any TEAE leading to dose reduction of trial treatment	xxx (xx.x)	xxx (xx.x)	xxx (xx.x)
Any trial treatment related TEAE leading to dose reduction of trial treatment	xxx (xx.x)	xxx (xx.x)	xxx (xx.x)

Note: TEAEs are defined as events that start within the day of first dose of trial treatment until 28 days after last dose of treatment.
Related TEAEs are events with relationship missing, unknown or related.

15.3: Safety Data

15.3.1: Display of Adverse Events

Table 15.3.1.3: TEAE by Primary System Organ Class (SOC) and Preferred Term (PT) - SAF Analysis Set

Primary System Organ Class Preferred Term	Treatment A N=xxx (100%) n (%)	Treatment B N=xxx (100%) n (%)	Treatment C N=xxx (100%) n (%)
Subjects with at least one event	xxx (xx.x)	xxx (xx.x)	xxx (xx.x)
SOC1	xxx (xx.x)	xxx (xx.x)	xxx (xx.x)
PT11	xxx (xx.x)	xxx (xx.x)	xxx (xx.x)
PT12	xxx (xx.x)	xxx (xx.x)	xxx (xx.x)
PT13	xxx (xx.x)	xxx (xx.x)	xxx (xx.x)
SOC2	xxx (xx.x)	xxx (xx.x)	xxx (xx.x)
PT21	xxx (xx.x)	xxx (xx.x)	xxx (xx.x)
PT22	xxx (xx.x)	xxx (xx.x)	xxx (xx.x)

MedDRA version 19.1.

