Treatment Arm: Treatment A, Subject ID: XXXXXXXXXX, Age: xx, Sex: X, Race: XXXXXXXX

Treatment Administration: First Date: DDMONYYYY, Last Date: DDMONYYYY, Number of infusions: xx

X	XXXXXXXXXXXXXXXXXX/ XXXXXXXXXXXXXXXXXX	DDMONYYYY/ DDMONYYYY	xx	During	Related	2	Reduced	Ong.	xx
---	---	-------------------------	----	--------	---------	---	---------	------	----

Treatment Arm: Treatment B, Subject ID: XXXXXXXXXX, Age: xx, Sex: X, Race: XXXXXXXX

Treatment Administration: First Date: DDMONYYYY, Last Date: DDMONYYYY, Number of infusions: xx

X	XXXXXXXXXXXXXXXXXX/ XXXXXXXXXXXXXXXXXX	DDMONYYYY/ DDMONYYYY	xx	After	Unrelated	3	Interrupted	Res. w. sequ.	xx
---	---	-------------------------	----	-------	-----------	---	-------------	---------------	----

MedDRA version 19.1, NCI-CTCAE version 4.03.

Note: (a) Action: No change = Dose not changed, Reduced = Dose reduced, Interrupted = Drug interrupted, Withdrawn = Drug withdrawn, N/A = Not applicable.

(b) Outcome: Change = Change in severity, Res. = Resolved, Res. w. sequ. = Resolved with sequelae, Ong. = Ongoing, Fatal = Fatal, Unknown = Unknown.

Programming note: MedDRA version 19.1 or highest at time of data transfer.

15.3: Safety Data

15.3.5: Clinical Laboratory Evaluations

Table 15.3.5.1: Hematology - Shift from Baseline to Worst On-treatment Value - SAF Analysis Set

Laboratory Test	Treatment	Baseline Classification	Worst On-treatment Value				Total n (%)
			Low n (%)	Normal n (%)	High n (%)	Missing n (%)	
PARAM1 (Unit1)	Treatment A N=XXX	Low	xxx (xx.x)	xxx (xx.x)	xxx (xx.x)	xxx (xx.x)	xxx (100.0)
		Normal	xxx (xx.x)	xxx (xx.x)	xxx (xx.x)	xxx (xx.x)	xxx (100.0)
		High	xxx (xx.x)	xxx (xx.x)	xxx (xx.x)	xxx (xx.x)	xxx (100.0)
		Missing	xxx (xx.x)	xxx (xx.x)	xxx (xx.x)	xxx (xx.x)	xxx (100.0)
		Total	xxx (xx.x)	xxx (xx.x)	xxx (xx.x)	xxx (xx.x)	xxx (100.0)
	Treatment B N=XXX	Low	xxx (xx.x)	xxx (xx.x)	xxx (xx.x)	xxx (xx.x)	xxx (100.0)
		Normal	xxx (xx.x)	xxx (xx.x)	xxx (xx.x)	xxx (xx.x)	xxx (100.0)
		High	xxx (xx.x)	xxx (xx.x)	xxx (xx.x)	xxx (xx.x)	xxx (100.0)
		Missing	xxx (xx.x)	xxx (xx.x)	xxx (xx.x)	xxx (xx.x)	xxx (100.0)
		Total	xxx (xx.x)	xxx (xx.x)	xxx (xx.x)	xxx (xx.x)	xxx (100.0)
.....							

Note: Baseline is the last measurement prior to the first dose of any trial treatment.
Normal category includes low values for high parameters and high values for low parameters.

Repeat table 15.3.5.1 for:

Table 15.3.5.2: Clinical Chemistry - Shift from Baseline to Worst On-treatment Value - SAF Analysis Set

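### The SAP addendum defines treatment-emergent events by start date alone and drops the protocol's worsening limb, so an adverse event that begins in screening and worsens on treatment can be missing from the TEAE tables

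*SAP*

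**What the plan says.** Protocol 7.4.1.1 gives a TEAE two limbs. The first is an event not present before the IMP was started. The second is "any event already present that worsens in either severity or frequency following exposure to the IMP". Protocol 8.3.3 makes the number of subjects with treatment-emergent AEs, SAEs and AESIs a safety endpoint.

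The SAP addendum prints a different rule under Tables 15.3.1.1, 15.3.1.2, 15.3.1.3 and 15.3.1.8: "TEAEs are defined as events that start within the day of first dose of trial treatment". The window closes 28 days after the last dose. Only the start date matters. SAP section 9, the place for changes to the protocol's planned analyses, points to later sections, and none of them mentions this change. SAP section 17 refers to the IDMC SAP for the safety summaries.

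Three further passages bear on how much this matters:

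- Protocol 7.4.1.3 starts AE reporting at the first consent signature, and 7.1.1 places eligibility assessment at a "Screening Visit that will occur within 42 days prior to Day 1". AE records can therefore start before dosing.
- Protocol 7.4.1.1 also keeps one group of findings out of AE reporting: "Medical conditions present at the initial trial visit that do not worsen in severity or frequency during the trial are defined as Baseline Medical Conditions".
- Footnote (b) of SAP Table 15.3.2.3 includes the outcome code "Change = Change in severity".

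**The concern.** The addendum narrows the definition of a protocol safety endpoint without saying so. An AE recorded in screening as mild that becomes Grade 3 or serious after dosing is treatment-emergent under the protocol. Under the footnote it need not be.

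This trial treats worsening as a signal in its own right. Under protocol 7.4.1.1, a Grade 1 or 2 cutaneous reaction that is getting worse is an AESI. Protocol 3.3 regards an increase in number or worsening of digital ulcers as the safety issue, because the disease itself causes ulcers. SAP section 16 plans no tests or confidence intervals for efficacy, so AE counts by arm carry much of the abbreviated report. A rule that can omit on-treatment worsening from those counts should not differ from the protocol unannounced.

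**Working it through.** The documents give no figure to reproduce. The check compares the two definitions case by case and then counts the outputs affected.

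**Step 1: apply each rule.** All post-dose changes below are taken to fall within 28 days of the last dose, so that only the opening of the window is at issue.

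| Case | Protocol 7.4.1.1 | SAP footnote |
|---|---|---|
| New event on treatment | TEAE | TEAE |
| AE starts in screening, does not worsen | Not a TEAE | Not a TEAE |
| AE starts in screening, severity worsens after dosing, same record kept | TEAE | Not a TEAE |
| AE starts in screening, becomes more frequent after dosing, same record kept | TEAE | Not a TEAE |
| AE starts in screening, severity worsens after dosing, new record opened at the change | TEAE | TEAE |
| AE starts in screening, improves after dosing, new record opened at the change | Not a TEAE | TEAE |
| Baseline condition first worsens after dosing, AE dated from the worsening | TEAE | TEAE |

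The rules disagree in three rows. In two of them the SAP misses an event. In the third it would count an improvement. Which rows occur depends on whether a change opens a new record, and no supplied passage states this. Protocol 7.4.1.2 asks for onset and resolution dates but gives no rule for a change in severity or frequency. It refers specific guidance to the eCRF Completion and Monitoring Conventions.

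**Step 2: count the outputs.** The footnote is printed under 4 tables. Tables 15.3.1.4 to 15.3.1.7 and 15.3.1.10 to 15.3.1.14 repeat the layout of Table 15.3.1.3 (4 + 5 = 9), and Table 15.3.1.9 repeats Table 15.3.1.8 (1). So 4 + 9 + 1 = 14, which is every table from 15.3.1.1 to 15.3.1.14. Table 15.3.2.3 is also limited to serious TEAEs. No table counts all AEs. Events that fail the test remain visible in Listing 16.2.7.1 (all AEs) and, if serious, in Listing 16.2.7.2, where they carry the non-treatment-emergent mark. Deaths in Table 15.3.2.1 are not restricted to TEAEs.

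**Step 3: weight of one misclassified subject.** The planned 500 mg arm is 175 × 1/5 = 35 subjects, so one subject is 1/35 = 2.9 percentage points. The other two arms are 175 × 2/5 = 70 each, so one subject is 1/70 = 1.4 points. SAP section 5 says the trial stopped early with limited numbers. If the 500 mg arm had 10 subjects (an assumption), one subject would be 1/10 = 10 points. These figures show the sensitivity of the tables and do not estimate how many events are lost.

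**The case against.** A reader might infer that worsening of pre-existing disease in general drops out of the AE tables. The documents do not support that. Footnote l of protocol Table 1 and footnote i of Table 2 have new or worsening digital ulcers captured as AEs. Protocol 6.5.5 has new or worsening scleroderma manifestations not measured elsewhere reported as AEs, with a dedicated eCRF question. Protocol 7.4.1.1 keeps a condition present at the initial visit out of AE reporting unless it worsens. For such conditions the worsening is the event, its natural start date is after dosing, and the footnote counts it. No passage says that an old condition is entered with its original onset date.

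The rest of the defence is as follows:

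- The outcome code for a change in severity suggests that one record may end and another begin when severity changes.
- The addendum relies on the Study SAP and the IDMC SAP, and the recording rules are in the eCRF conventions. None of these was available for this review, and any of them could hold a fuller rule.
- The by-subject listings still show every event, and in a small terminated trial they will be read.

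Most of this stands, and it limits the reach of the point, but it does not remove it. An AE already recorded in screening is not a baseline condition waiting to become an AE, so the argument about baseline disease does not cover it. The severity code does not cover frequency. The listings give no counts by arm, and the SAE listing would label a worsened pre-dose SAE contrary to the protocol. A fuller definition elsewhere would contradict the footnote printed on the outputs.

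**Conclusion.** The footnote departs from protocol 7.4.1.1, and the addendum does not declare it. The exposure is mainly to AEs that start between consent and first dose, a span of up to 42 days, and then worsen on treatment under the original record or only in frequency. Such an event would be missing from all 14 TEAE tables and the serious TEAE display, and would be mislabelled in Listing 16.2.7.2 if serious.

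The number of such events cannot be worked out from the documents. It may be small or zero. The conclusion assumes that at least some pre-dose records stay open through a worsening, which the documents neither state nor exclude. The broader inference, that worsening of baseline skin, ulcer or gastrointestinal disease is lost, is not supported. The point is a definition to align before database lock and is not evidence that the safety tables are unreliable. It concerns only the opening of the window; the 28-day close is a separate matter.

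**What to change.** Restate the footnote and the TEAE flag in the protocol's terms: an event is treatment-emergent if it starts on or after the day of first dose, or was present before it and became worse in severity or frequency afterwards.

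The AE shells hold one start date and one grade per record, so the derivation needs two routes:

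1. Where a worsening was entered as a new record, flag that record by its own start date. Do not flag a record that shows only improvement on a pre-dose event.
2. Where a pre-dose record was kept open, identify post-dose worsening at the blinded data review that SAP section 8.1 already schedules before database lock. Its stated purpose is protocol deviations, so this is an added item. Frequency is not among the AE report contents listed in protocol 7.4.1.2, so worsening in frequency will also need to be looked for there.

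If the team prefers the start-date rule, section 9 should declare it as a departure and state how a worsening is recorded.

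The cost is the footnote wording, one derivation in the AE dataset, and a small amount of data review limited to AEs with onset before first dose.

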18.2 Listings

16.2.1: Subject Disposition

Listing 16.2.1.1: Subject Disposition and Withdrawals - Screening Analysis Set

Treatment Group	Subject Identifier	Screening Date	Randomized?/ Date Randomized/ Stratification Factor (a)	Withdrew Prior to Being Treated?	In SAF Analysis Set?	Withdrew from trial treatment/ Reason for Withdrawal	Date of Last Dose	Discont- inued Trial?/ Primary Reason	Date Discont- inued
Treatment A	XXXXXXX	DDMMYYYY	Yes/DDMMYYYY/ FVC <70%	XXX	XXX	Yes/XXXXXXXX XXXX	DDMMYYYY	Yes/ xxxxxxx	DDMMYYYY
	XXXXXXX	DDMMYYYY	Yes/DDMMYYYY/ FVC ≥70%	XXX	XXX	No		No	
	XXXXXXX	DDMMYYYY	Yes/DDMMYYYY/ XXXXXX	XXX	XXX	No		No	
								
Treatment B	XXXXXXX	DDMMYYYY	Yes/DDMMYYYY/ XXXXXX	XXX	XXX	No		No	
	...								
Etc.									

(a) Stratification Factor from eCRF: FVC <70% = Baseline FVC <70% predicted, FVC ≥70% = Baseline FVC ≥70% predicted.
Note: Baseline is defined as the last non-missing assessment value prior to randomization.

Programming Note: If a subject is screened but not yet randomized, treatment group will be Not Randomized. If they are screen failed then treatment group is Screen Failures.
If there are subjects in the Not Randomized group then add the following footnote (note indentation to line up with baseline footnote):

'Not Randomized' treatment group contains subjects who are still in screening at time of data cutoff.
Ensure any "Other" reasons for treatment and trial termination are specified, "Other: xxxxxx".

16.2.1: Subject Disposition
Listing 16.2.2.1: Important Protocol Deviations - ITT Analysis Set

Treatment Group	Subject Identifier	Type	Deviation details
Treatment A	XXXXXXX	Eligibility and Entry Criteria	XXXXXXXXXXXXXXXXX/ XXXXXXXXXXXXXXXXXXXXX
		Efficacy Criteria	XXXXXXXXXXXXXXXXXXXXX
	XXXXXXX	XXXXXXXXXXXXX	XXXXXXXXXXXXXXXXXXXXX
	XXXXXXX	XXXXXXXXXXXXX	XXXXXXXXXXXXXXXXXXXXX
		XXXXXXXXXXXXXXXXXXXXX
Treatment B	XXXXXXX	XXXXXXXXXXXXX XXXXXXXXXXXXX	XXXXXXXXXXXXXXXXXXXXX XXXXXXXXXXXXXXXXXXXXX
Etc.	...		

Programming note: Present each deviation on a new line.

16.2.4: Demographic Data
Listing 16.2.4.1: Subject Demographics - SAF Analysis Set

Treatment Group	Subject Identifier	Sex	Birth Date	Age (years)	Race	Ethnicity
Treatment A	XXXXXXX	Male	DDMMYYYY	XX	XXXXXXX	XXXXX
	XXXXXXX	Female	YYYY	XX	XXXXXXX	XXXXX
	XXXXXXX	XXXX	DDMMYYYY	XX	XXXXXXX	XXXXX
					
Treatment B	XXXXXXX	XXXX	DDMMYYYY	XX	XXXXXXX	XXXXX
	...					
Etc.						

Note: Age is relative to the date of informed consent.

16.2.4: Demographic Data

Listing 16.2.4.2: Subject Medical History - SAF Analysis Set

Treatment Group	Subject Identifier	System Organ Class	Preferred Term	Verbatim Text	Start Date	End Date	Related to Study Condition?
Treatment A	XXXXXXX	XXXXXXX	XXXXXXX	XXXXXXX	DDMMYYYY	Ongoing	Yes
		XXXXXXX	XXXXXXX	XXXXXXX	DDMMYYYY	DDMMYYYY	No
		XXXXXXX	XXXXXXX	XXXXXXX	DDMMYYYY	XXXXXXXX	Unknown
.....							
Treatment B	XXXXXXX	XXXXXXX	XXXXXXX	XXXXXXX	DDMMYYYY	XXXXXXXX	
...							
Etc.							

MedDRA version xx.x.

Programming note: MedDRA version 19.1 or highest at time of data transfer.

16.2.4: Demographic Data

Listing 16.2.4.3: Subject Disease History - SAF Analysis Set

Treatment Group	Subject Identifier	Date of Diagnosis	Time Since Date of Diagnosis (years)	Status	Systemic Sclerosis Symptom History (a)	ACR/EULAR Classification Criteria for Systemic Sclerosis (b)
Treatment A	XXXXXXX	DDMMYYYY	XX.XX	Diffuse cutaneous SSc	Skin Thickening/ Tendon friction rubs/ XXXXXXX	Fingertip lesions: Fingertip pitting scars/ Abnormal nailfold capillaries/ XXXXXX
	XXXXXXX	DDMMYYYY	XX.XX	Limited cutaneous SSc	XXXXXXX/ XXXXXXXX / XXXXXXXXXX/ XXXXXXX	XXXXXXX/ XXXXXXXX / XXXXXXXXXX/ XXXXXXX
	XXXXXXX	DDMMYYYY	XX.XX	XXXXXXX	XXXXXXX/ XXXXXXXX / XXXXXXXXXX/ XXXXXXX	XXXXXXX/ XXXXXXXX / XXXXXXXXXX/ XXXXXXX
					
Treatment B	XXXXXXX	DDMMYYYY	XX.XX	XXXXXXXXX	XXXXXXX/ XXXXXXXX / XXXXXXXXXX/ XXXXXXX	
	...					

Etc.

(a) Where 'Yes' was selected on the eCRF.

(b) Where 'Present' was selected on the eCRF.

Note: Time since date of diagnosis is relative to date of informed consent.

Programming note: Concatenate all Systemic Sclerosis Symptom History sub-categories where 'Yes' is ticked on the eCRF, concatenate all ACR/EULAR Classification Criteria for Systemic Sclerosis sub-categories where 'Present' is ticked on the eCRF.

16.2.4: Demographic Data

Listing 16.2.4.4: Previous Medications - SAF Analysis Set

Treatment Group	Subject Identifier	ATC Level 2/ Preferred Term/ Reported Name	Start Date/ End Date (Trial Day)	Dose (Unit)	Frequency	Route	Reason (Indication)	Reason(s)
Treatment A	XXXXXXX	XXXXXXXXXXXXX/ XXXXXXXXX/ XXXXXXXXX	DDMMYY (xx) / DDMMYY (xx)	XXX xx	XX	XX	XXXXXXXXX	Adverse event/ Disease related condition
		XXXXXXXXXXXXX/ XXXXXXXXX/ XXXXXXXXX	DDMMYY (xx) / DDMMYY (xx)	XXX xx	Other: XXX	XX	XXXXXXXXX	XXXXXXXXX
							
Treatment B	XXXXXXX	XXXXXXXXXXXXX/ XXXXXXXXX/ XXXXXXXXX	DDMMYY (xx) / DDMMYY (xx)	XXX	XX	Other: XX	XXXXXXXXXXXXX	XXXXXX
	...							
Etc.								

WHO Drug Dictionary version Enhanced September 2016.

Note: In case multiple ATCs are assigned to a medication, all ATCs will be reported.

Programming note: WHO Drug Dictionary version Enhanced September 2016 or highest at time of data transfer.

Repeat listing 16.2.4.4 for:

Listing 16.2.4.5: Concomitant Medications - SAF Analysis Set

Change "Previous Medication" to "Concomitant Medication"

Listing 16.2.4.6: Background Therapy - SAF Analysis Set

Change "Previous Medication" to "Background Therapy".

16.2.5: Treatment Compliance and Exposure

Listing 16.2.5.1: Trial Treatment Administration Details - SAF Analysis Set

Treatment Group	Subject Identifier	Visit	Preparation Date (Time) / Kit Number	Admin. Start Date (Time) / End Date (Time)	Duration of infusion (hours)	Change in Dose?	Planned Volume (mL)	Actual Volume (mL)	Infusion Completed as Planned?
A	XXXXXXX	XXXXXXX	DDMMYY (HH:MM) / XXXX	DDMMYY (HH:MM) / DDMMYY (HH:MM)	XX.XX	No	XXX	XXX	No: Adverse event
		XXXXXXX	DDMMYY (HH:MM) / XXXX	DDMMYY (HH:MM) / DDMMYY (HH:MM)	XX.XX	Dose adjusted: Adverse event	XXX	XXX	Yes
		XXXXXXX	DDMMYY (HH:MM) / XXXX	DDMMYY (HH:MM) / DDMMYY (HH:MM)	XX.XX	XXXXXXX	XXX	XXX	XXX
		XXXXXXX*				No dose: Missed visit	XXX		No: Other, No dose: missed visit

Etc.

* = Visit derived due to the subject not completing the "STUDY TREATMENT ADMINISTRATION DETAILS" eCRF page at the missed visit.

Note: Admin. = Administration.

Duration of infusion is calculated as: End time of administration - start time of administration.

16.2.5: Treatment Compliance and Exposure

Listing 16.2.5.2: Overall Exposure to Trial Treatment - SAF Analysis Set

Treatment Group	Subject Identifier	Treatment Duration (weeks)	Number of Infusions	Number of Dose Adjustments	Number of Infusions Not Completed as Planned	Overall Treatment Adherence (%)
Treatment A	XXXXXXX	XXX	XX	X	X	XX

Etc.

Note: Treatment duration is calculated as: (Last infusion date prior to data cut-off - first infusion date + 28) / 7 days.

Subject overall treatment adherence is calculated as: (sum of actual volume received/ sum of planned Volume, up to and including their last dose recorded on their treatment termination visit)*100.

16.2.6: Efficacy Data

Listing 16.2.6.1: FVC Volume (mL) and FVC % Predicted - mITT Analysis Set

Treatment Group	Subject Identifier	Visit	Date of Assessment (Trial Day)	FVC (mL)		FVC % Predicted	
				Observed	Change from Baseline	Observed	Change from Baseline
Treatment A	XXXXXXXX	XXXXXXXX	DDMMYYYY (xx)	XX*		XX*	
		XXXXXXXX	DDMMYYYY (xx)	XX	XX	XX	XX
		XXXXXXXX	DDMMYYYY (xx)	XX	XX	XX	XX

Etc.

* Baseline value.

Note: Baseline is defined as the last non-missing assessment value prior to randomization. If such a value is missing then the last value prior to the first trial treatment administration will be used.

Trial day is defined relative to the date of randomization.

16.2.6: Efficacy Data

Listing 16.2.6.2: mRSS Total Score - mITT Analysis Set

Treatment Group	Subject Identifier	Visit	Date of Assessment (Trial Day)	mRSS Total Score	
				Observed	Change from Baseline
Treatment A	XXXXXXX	XXXXXXX	DDMMYYYY (xx)	XX*	
		XXXXXXX	DDMMYYYY (xx)	XX	XX
		XXXXXXX	DDMMYYYY (xx)	XX	XX

Etc.

* Baseline value.

^ = diffuse cutaneous systemic sclerosis at baseline.

Note: Baseline is defined as the last non-missing assessment value prior to randomization. If such a value is missing then the last value prior to the first trial treatment administration will be used.
Trial day is defined relative to the date of randomization.

16.2.6: Efficacy Data

Listing 16.2.6.3: Clinically Meaningful Disease Progression - mITT Analysis Set

Treatment Group	Subject Identifier	Date of Progression (Trial Day)	Progression Criteria Fulfilled	SSc-ILD progression		Was the Trial Treatment Discontinued?
				Was Mycophenolate Dose Increased?	Was a New Immunosuppressant or Biologic Drug Initiated?	
Treatment A	XXXXXXX	DDMMYYYY (xx)	SSc-ILD: Relative decrease from baseline in FVC % predicted >10% SSc other than ILD: Scleroderma renal crisis	No	No	No
		DDMMYYYY (xx)				XX

Etc.

Note: Trial day is defined relative to the date of randomization.

Programming note: Only display subjects with clinically meaningful disease progression. Concatenate all details selected for SSc other than ILD (including the free text details for 'Other'). If both SSc-ILD and SSc other than ILD were selected on the same date, then display on a new line.

16.2.6: Efficacy Data
Listing 16.2.6.4: DLCO - mITT Analysis Set

Treatment Group	Subject Identifier	Visit	Date of Assessment (Trial Day)	DLCO as recorded on eCRF		DLCO Result in SI Unit (mmol of CO/min/kPa)		DLCO % Predicted	
				Observed (unit)		Observed	Change from Baseline	Observed	Change from Baseline
Treatment A	XXXXXXXX	XXXXXX	DDMMYYYY (xx)	XX (xxx)		XX*		XX*	
		XXXXXX	DDMMYYYY (xx)	XX (xxx)		XX	XX	XX	XX
		XXXXXX	DDMMYYYY (xx)	XX (xxx)		XX	XX	XX	XX

Etc.

* Baseline value.
Note: Baseline is defined as the last non-missing assessment value prior to randomization. If such a value is missing then the last value prior to the first trial treatment administration will be used.
Trial day is defined relative to the date of randomization.

16.2.6: Efficacy Data
 Listing 16.2.6.5: KCO - mITT Analysis Set

Treatment Group	Subject Identifier	Visit	Date of Assessment (Trial Day)	Test overread grading	VA	DLCO/ VA	KCO	
							Observed	Change from baseline
Treatment A	XXXXXXXX	XXXXXXXX	DDMMYYYY (xx)	Acceptable	xx	xx+	xx*	
		XXXXXXXX	DDMMYYYY (xx)	Unacceptable	xx	xx	xx	xx
		XXXXXXXX	DDMMYYYY (xx)	xxxxx				

Etc.

* Baseline value.

Note: Baseline is defined as the last non-missing assessment value prior to randomization.
 Trial day is defined relative to the date of randomization.

16.2.6: Efficacy Data
Listing 16.2.6.6: Digital Ulcers - mITT Analysis Set

Treatment Group	Subject Identifier	Visit	Completed Status	Date of Assessment (Trial Day)	Number of						Total Digital Ulcer count
					Active Ulcers		Undetermined Ulcers		Healed Ulcers		
					Absolute Value	CFB	Absolute Value	CFB	Absolute Value	CFB	
Treatment A	XXXXXXXX	XXXXXX	Done	DDMMYYYY (xx)	XXX*		XXX*		XXX*		XXX
		XXXXXX	Not Done								
		XXXXXX	XXXXXXXX	DDMMYYYY (xx)	XXX	XXX	XXX	XXX	XXX	XXX	XXX

Etc.

* Baseline value.
Note: Baseline is defined as the last non-missing assessment value prior to randomization.
CFB = Change from Baseline.
Trial day is defined relative to the date of randomization.

16.2.6: Efficacy Data

Listing 16.2.6.7: Mahler BDI/TDI - mITT Analysis Set

Treatment Group	Subject Identifier	Visit	Date of Assessment (Trial Day)	Done/ Not done - Reason	Question	Score		
Treatment A	XXXXXXX	XXXXXXX	DDMMYYYY (xx)	Done	Functional Impairment	x		
					Magnitude of Task	x		
					Magnitude of Effort	x		
							Total	x
			XXXXXXX	DDMMYYYY (xx)	Done	Changes in Functional Impairment	x	
		Changes in Magnitude of Task				x		
		Changes in Magnitude of Effort				x		
						Total	x	
			XXXXXXX	DDMMYYYY (xx)	Not done - Subject felt too ill			

Etc.

Note: Baseline is defined as the last non-missing assessment value prior to randomization. The BDI is completed at baseline and the TDI is completed at subsequent visits.
Trial day is defined relative to the date of randomization.

16.2.6: Efficacy Data

Listing 16.2.6.8: SGRQ - Question Scores - mITT Analysis Set

Treatment Group	Subject Identifier	Visit	Date of Assessment (Trial Day)	Done/ Not done - Reason	Question (component)	Answer(s)	Weight	
Treatment A	XXXXXXXX	XXXXXXXX	DDMMYYYY (xx)	Done	xxxxxx (S)	xxxx	x	
					xxxxxx (I)	xxxx	x	
					xxxxxx	xxxx	x	
						...	xxxxxx	x
		XXXXXXXX	DDMMYYYY (xx)	Done	xxxxxx	xxxx	x	
					xxxxxx	xxxxxx	x	
					xxxxxx	xxxx	x	
		XXXXXXXX	DDMMYYYY (xx)	Not done - Subject felt too ill	xxxxxx	xxxxxx	x	

Etc.

Note: Component abbreviations: S = Symptoms, I = Impacts, A = Activity.
Trial day is defined relative to the date of randomization.

16.2.6: Efficacy Data

Listing 16.2.6.9: SGRQ - Component and Total Scores - mITT Analysis Set

Treatment Group	Subject Identifier	Visit	Date of Assessment (Trial Day)	Done/ Not done - Reason	Component	Score	Change from baseline
Treatment A	XXXXXXX	XXXXXXX	DDMMYYYY (xx)	Done	Symptoms	x	
					Activity	x	
					Impacts	x	
					Total	x*	
		XXXXXXX	DDMMYYYY (xx)	Done	Symptoms	x	
					Activity	x	
XXXXXXX	DDMMYYYY (xx)	Not done - Subject felt too ill	Impacts	x			
			Total	x	x		

Etc.

* Baseline value (total scores only).

Note: Baseline is defined as the last non-missing measurement prior to randomization.

Trial day is defined relative to the date of randomization.

The component score is 100 x summed weights from all positive items in that component divided by the sum of weights for all items in that component. The total score is 100 x summed weights from all positive items in the questionnaire divided by the sum of weights for all items in the questionnaire.

16.2.6: Efficacy Data

Listing 16.2.6.10: Leicester Cough Index - Question Scores - mITT Analysis Set

Treatment Group	Subject Identifier	Visit	Date of Assessment (Trial Day)	Done/ Not done - Reason	Question (domain)	Score
Treatment A	XXXXXXXX	XXXXXXXX	DDMMYYYY (xx)	Done	xxxxxx (P)	x
					xxxxxx (Psy)	x
					xxxxxx (S)	x
		XXXXXXXX	DDMMYYYY (xx)	Done	xxxxxx	x
					xxxxxx	x
						x
XXXXXXXX	DDMMYYYY (xx)	Not done - Subject felt too ill		x		

Etc.

Note: Trial day is defined relative to the date of randomization.
 Domain abbreviations: P = Physical, Psy = Psychological, S = Social.
 1 is the most negative score, 7 is the most positive score.

16.2.6: Efficacy Data

Listing 16.2.6.11: Leicester Cough Index - Domain and Total Scores - mITT Analysis Set

Treatment Group	Subject Identifier	Visit	Date of Assessment (Trial Day)	Done/ Not done - Reason	Domain	Score	Change from baseline
Treatment A	XXXXXXX	XXXXXXX	DDMMYYYY (xx)	Done	Physical	x	
					Psychological	x	
					Social	x	
					Total	x*	
		XXXXXXX	DDMMYYYY (xx)	Done	Physical	x	
					Psychological	x	
					Social	x	
		XXXXXXX	DDMMYYYY (xx)	Not done - Subject felt too ill	Total	x	x

Etc.

* Baseline value (total score only).

Note: Baseline is defined as the last non-missing assessment value prior to randomization.

Trial day is defined relative to the date of randomization.

Domain scores are the sum of all scores in the domain divided by the number of questions within that domain.

16.2.6: Efficacy Data

Listing 16.2.6.12: Physician's Global Assessment - mITT Analysis Set

Treatment Group	Subject Identifier	Visit	Date of Assessment (Trial Day)	Done/ Not done - Reason	Score	Change from baseline
Treatment A	XXXXXXX	XXXXXXX	DDMMYYYY (xx)	Done	x*	
		XXXXXXX	DDMMYYYY (xx)	Done	x	x
		XXXXXXX	DDMMYYYY (xx)	Not done - Subject felt too ill		

Etc.

* Baseline value.

Note: Baseline is defined as the last non-missing assessment value prior to randomization. Trial day is defined relative to the date of randomization.

The score is based on the question: "On a scale of 0-100, where would you rate the overall effect systemic sclerosis has on your patient at this time", where 0 = has no effect at all and 100 = worst possible effect.

Repeat listing 16.2.6.12 for:

Listing 16.2.6.13: Patient's Global Assessment - mITT Analysis Set

Update footnote: The score is based on the question: "On a scale of 0-100, where would you rate the overall effect systemic sclerosis has on you at this time", where 0 = has no effect at all and 100 = worst possible effect.

16.2.6: Efficacy Data

Listing 16.2.6.14: SHAQ - VAS Scores - mITT Analysis Set

Treatment Group	Subject Identifier	Visit	Overall disease activity		Raynaud's phenomenon		Finger ulcers		Breathing problems		Intestinal problems	
			Observed	CFB	Observed	CFB	Observed	CFB	Observed	CFB	Observed	CFB
Treatment A	XXXXXXXX	XXXXXX	xx*		xx*		xx*		xx*		xx*	
		XXXXXX	xx	xx	xx	xx	xx	xx	xx	xx	xx	xx
		XXXXXX	xx	xx	xx	xx	xx	xx	xx	xx	xx	xx
		XXXXXX	xx	xx	xx	xx	xx	xx	xx	xx	xx	xx
		...										
	XXXXXXXX	XXXXXX	xx^		xx^		xx^		xx^		xx^	
		XXXXXX	xx	xx	xx	xx	xx	xx	xx	xx	xx	xx
		XXXXXX	xx	xx	xx	xx	xx	xx	xx	xx	xx	xx
		XXXXXX	xx	xx	xx	xx	xx	xx	xx	xx	xx	xx
		...										
	XXXXXXXX	XXXXXX	xx		xx		xx		xx		xx	

Etc.

* Baseline value.

Note: Baseline is defined as the last non-missing assessment value prior to randomization.

The VAS scores range from 0 (most positive response) to 100 (most negative response).

